1.4.2 Risks

1.4.2.1 Elevated Creatine Kinase

Subjects with PMM may have asymptomatic benign raised baseline creatine kinase (CK) levels as part of the PMM disease. Even among healthy individuals CK levels rise transiently after exercise or intense physical activity. In patients with PMM, serum CK levels may increase to as much as 30 times the ULN within 24 hours after strenuous physical activity, then slowly decline over the next 7 days. The degree of CK elevation depends on the type and duration of exercise, with greater elevation in those who are untrained ([Moghadam-Kia, Oddis, & Aggarwal, 2016](#)). It is possible that improvements in the cellular energy deficit with REN001 treatment may result in increased muscle use and transient benign muscle enzyme elevations.

Serum CK data from subjects with PMM in the Phase 1b study (REN001-101) demonstrated a pattern of transient, elevated CKs following exercise and the collection of muscle biopsies; none of these elevations were associated with myoglobinuria. The elevations seen were self-limited and resolved with no intervention despite continued treatment with REN001 and continuation of the subject's normal activities of daily living, including exercise. In all clinical trials of REN001 to date, elevations in CK tended to be modest and reversible and were usually determined by investigators as unlikely to be associated with REN001 treatment. In the current study as a precautionary measure CK levels will be assessed throughout the study.

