3.7.1 Safety Monitoring for Muscle Injury

Patients with PMM often present with mild to moderate baseline elevations in CK and can experience transient episodes of significantly elevated CK induced by acute illness, vigorous exercise, and other conditions. These elevations are not associated with symptoms or signs and the patients are typically well. CK elevations are generally of the skeletal muscle

fraction. However, a small proportion of the total CK may be from the myocardial fraction reflecting a small amount of this fraction found in skeletal muscle rather than the presence of myocardial injury. Importantly, these elevations are entirely to be expected in this patient population with underlying muscle disease and are not synonymous with clinically significant rhabdomyolysis. Similarly, elevations in serum aminotransferases and uric acid can accompany CK elevations and may not be indicative of liver disease.

True, clinically significant, rhabdomyolysis may also occur in these patients and must be managed appropriately. Rhabdomyolysis is characterized by severe acute muscle injury resulting in muscle pain, weakness, and/or swelling with release of myofiber contents into the bloodstream. Symptoms develop over hours to days following a triggering event and may be associated with dark pigmentation of the urine ([Nance & Mammen, 2015](#)). Acute kidney injury is a complication of rhabdomyolysis. The risk of acute kidney injury is low in patients with CK levels less than 15,000 international units per liter (IU/L). The CK algorithm below has been designed to identify those subjects potentially at risk of true rhabdomyolysis and ensure appropriate early action is taken to monitor and treat the subjects accordingly.

Figure 2: CK Algorithm

For the purpose of the different enrollment options, baseline is considered the visit where the subject starts drug.

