3.2.2. Secondary Endpoints

- Absolute values, changes from Baseline and incidence of potentially clinically significant changes in:

- Laboratory safety tests
- Electrocardiograms (ECGs)
- Vital signs
- Eye assessments

For mtDNA-PMM subjects

- Absolute values and changes from Baseline in:
 - Distance walked during the 12-minute walk test (12MWT)*
 - Modified Fatigue Impact Scale (MFIS) Total scores and sub-scale scores*
 - Patient Global Impression of Severity (PGIS) score for fatigue and muscle symptoms
 - Brief Pain Inventory (BPI) pain severity and pain interference scores*
 - Patient-Reported Outcomes Measurement Information System (PROMIS) Short Form – Functional Assessment of Chronic Illness Therapy (FACIT) Fatigue 13a scores*
 - 36 Item Short Form Survey (SF-36) domain scores (7-day recall)*
 - Work Productivity and Activity Impairment questionnaire: Specific Health Problem (WPAI:SHP) scores*
 - First 6-minute walk distance and last 6-minute walk distance*
 - Phenotypic description questions
- Patient Global Impression of Change (PGIC) scores (muscle and fatigue symptoms)

**Collected up to Month 24 only.*

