Subjects who satisfy the criteria for values of potential clinical importance (PCI), identified in the table below, will be summarized and listed. The summary will present the number of subjects with at least one on-treatment post baseline value (including unscheduled visits) satisfying the criteria. The listing will have a similar layout to the overall laboratory listing but will only include those subjects who satisfy the criteria for a specific parameter. The records satisfying the criteria will be identified on the listing. The criteria are:

Category	Parameter	Criteria
Chemistry	Creatine kinase (CK)	Normal baseline value and post $\geq 5 \times$ ULN > ULN baseline value and post $\geq 5 \times$ baseline level
	Aldolase	Normal baseline value and post > ULN
	Troponin I	> ULN
	Potential Hy's Law (ALT, AST, total bilirubin and alkaline phosphatase)	ALT or AST > 3 x ULN and Total bilirubin > 2 x ULN and Alkaline Phosphatase $\leq 2 \times$ ULN

An evaluation of Drug-Induced Serious Hepatotoxicity (eDISH) plot will be generated. The plot will include all post baseline data and will present ALT relative to the upper limit of normal (ULN) on the x-axis and total bilirubin relative to the ULN on the y-axis using a log scale for both axes. Reference lines for Hy's law thresholds, i.e., ALT = 3 x ULN and total bilirubin = 2 x ULN, will be added. The plot will identify group and mutational group and separate plots will be done for on-treatment and off-treatment records.

A spaghetti plot for the changes from baseline in creatine kinase (CK) over time will be presented. The actual sampling day will be used on the x-axis (baseline will be set to day 1). A solid line will be used to connect measurements; however, if the measurement was collected after the last dose of study drug plus one day, then a dotted line will be used. Group will be identified on the plot. The plot will be repeated for aldolase and troponin I. Individual CK, aldolase, ALT, AST and troponin I values relative to the ULN will be plotted over time (i.e., one plot per subject) and group and mutation type will be identified.

The actual sampling day will be used on the x-axis (baseline will be set to day 1). The day of last dose of study drug will be identified on the plot with a vertical reference line.

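### In the SAP 12.2 table of potentially important laboratory values, the troponin I row counts elevations present before dosing, and the aldolase row can never count a subject who starts above normal

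*SAP*

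**What the plan says.** The secondary endpoints (SAP 3.2.2, matching Protocol 3.2.2) include, for laboratory safety tests, "Absolute values, changes from Baseline and incidence of potentially clinically significant changes in" those tests. SAP 12.2 supplies the incidence part through a table of PCI criteria: "The summary will present the number of subjects with at least one on-treatment post baseline value (including unscheduled visits) satisfying the criteria".

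The three muscle-marker rows treat baseline differently:

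- **CK** has two branches. A subject with a normal baseline is flagged at 5 x ULN or more; a subject with a baseline above ULN is flagged at 5 x that baseline or more.
- **Aldolase** has one branch: "Normal baseline value and post > ULN".
- **Troponin I** has no baseline condition: "Troponin I > ULN".

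Three other provisions matter. SAP 8.6 takes baseline as the last non-missing assessment before dosing. SAP 8.2 sets the default percentage base at all subjects in the analysis set with non-missing data, and 12.2 does not override it. SAP 6 keeps the extra Month 9 and Month 15 visits at German sites out of by-visit summaries but lets them into the PCI summary. I found no reason given for the different handling of baseline.

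**The concern.** An incidence of changes should count subjects who got worse and leave out those who did not. The troponin I row fails on the second requirement: a subject above ULN before the first dose is counted if the marker stays the same, or even if it falls, provided it remains above ULN. The aldolase row fails on the first: a subject above ULN at baseline has no route into the count, however far the value rises.

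The two faults pull in opposite directions. The troponin I count is inflated by pre-existing elevation. The aldolase count leaves out the raised-baseline subjects, and any percentage on the default base is diluted by people who could not have been counted.

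What is at stake is the reading of the muscle-injury laboratory data in a study whose primary objective is long-term safety. Laboratory change linked to clinically significant muscle events is also one of the three types of adverse event of special interest. REN001-202 has no concurrent control, so a reader cannot calibrate either count against an untreated group.

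The aldolase gap has one further consequence. In the presentation from the start of REN001-202, subjects who took mavodelpar in REN001-201 and rolled over at Week 24 have an on-drug baseline. If their aldolase had already risen above ULN on drug, they drop out of that count. The presentation from the start of REN001 treatment uses the earlier baseline and so softens this, but the missing branch remains.

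**Working it through.** There is no stated figure to reproduce; the check is to apply the rules as written.

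**Rules, in multiples of ULN** (b = baseline, p = an on-treatment post-baseline value):

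- Aldolase: counted if b ≤ 1 and p > 1.
- Troponin I: counted if p > 1.
- CK, for comparison: counted if p ≥ 5 x max(1, b).

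| b | p | What happened | Aldolase | Troponin I | CK |
|---|---|---|---|---|---|
| 0.99 | 1.01 | 2% rise across ULN | counted | counted | no |
| 1.5 | 1.5 | no change | no | counted | no |
| 2 | 1.5 | fall | no | counted | no |
| 1.01 | 4 | about fourfold rise | no | counted | no |
| 1.01 | 10 | about tenfold rise | no | counted | counted |

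Aldolase counts the 2% rise and misses the tenfold one. Troponin I counts no change, a fall and a tenfold rise alike. CK separates them.

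**Do the other outputs fill the gap?**

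- *Shift tables (SAP 12.2)* separate normal-to-high from high-to-high, which helps for troponin I. But they work visit by visit, and a rise within the high category does not show.
- *By-visit data (SAP 8.4)* use the scheduled on-treatment assessment whenever it lies in the window, whatever unscheduled values lie there too. A peak at an unscheduled visit can be passed over. German Month 9 and 15 samples are excluded (SAP 6).
- *Change-from-baseline summaries* give means, medians and extremes by visit, not a count of subjects who worsened.
- *Box plots* include CK but neither aldolase nor troponin I.
- *Spaghetti plots and individual plots* cover all three markers but yield no incidence.
- *Listings:* the full laboratory listing shows everything. The PCI listing is limited to subjects who meet a criterion, so a raised-baseline aldolase subject is absent from it too.

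Only the PCI summary counts subjects over all on-treatment values, including unscheduled and German Month 9/15 samples. The gap is therefore real, but confined to that count.

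**Illustrative size.** The documents give no proportion with raised baseline aldolase or troponin I, so these are assumptions. Let q be the share with a raised baseline and r the risk of a new elevation among the rest.

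- *Aldolase, subjects who cannot be counted:* 200 x q, with 200 = about 150 mtDNA plus up to 50 nDNA. For q = 5% to 50%: 10 to 100.
- *Aldolase, reported rate on the default base:* r x (1 − q). With r = 10% and q = 10%, 30%, 50%: 9%, 7%, 5%, against 10% over eligible subjects.
- *Troponin I, counted without any change:* 200 x q. For q = 5% to 20%, all stable: 10 to 40.
- *Troponin I, pre-existing share of the count:* q / [q + (1 − q) x r]. With r = 5%:
  - q = 5%: 0.05 / (0.05 + 0.0475) = 51%
  - q = 10%: 0.10 / (0.10 + 0.045) = 69%
  - q = 20%: 0.20 / (0.20 + 0.04) = 83%

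The two mutation groups are summarised separately, so the pooled 200 only indicates scale.

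**The case against.** The strongest reply has four parts.

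*The table is about values, not changes.* SAP 12.2 labels it that way, and Protocol 8.6 also speaks of clinically significant values. On that reading, troponin I above ULN is a legitimate count. But the endpoint in both documents is worded as changes, and the table's own CK and aldolase rows condition on baseline, so it is not consistently a table of values.

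*Nothing is hidden.* Shift tables, change summaries, plots and listings let a careful reader find any subject. This stands, and it limits the seriousness of the point. It does not supply the incidence.

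*The primary endpoints do not depend on these flags.* They are adverse-event counts; muscle-injury events of special interest are identified on the case report form, and clinically significant laboratory results are reported as adverse events. This also stands. That a reader would take the troponin I count as a drug effect is a possibility, not something the documents show.

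*Raised baselines may be rare.* The protocol says raised baseline CK is common in this disease but says nothing of the kind about aldolase or troponin I. So the size is unknown, though the logic of the rows does not depend on it.

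A reader might also infer that the CK rows are faulty, since a raised-baseline flag scales with one pre-dose value and the protocol notes that "serum CK levels may increase to as much as 30 times the ULN within 24 hours after strenuous physical activity". A baseline of 30 x ULN would put the flag at 5 x 30 = 150 x ULN. A baseline above 15,000 / 5 = 3,000 IU/L would put it above the 15,000 IU/L that Protocol 3.7.1 mentions in connection with kidney risk. The documents do not support calling this an error. Scaling to baseline is a defensible choice where raised CK is expected. Nothing indicates that baseline draws follow strenuous exercise. The 15,000 IU/L figure is background, not an analysis threshold. The CK algorithm figure is not available, so agreement with it cannot be checked.

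**Conclusion.** The point holds for two rows. Troponin I mixes new elevations with unchanged or falling ones. Aldolase leaves out every subject with a raised baseline while the default base keeps them in. Both follow directly from the criteria as written, without assumption. How many subjects are affected cannot be determined from the documents; the ranges above rest wholly on assumed baseline prevalences and new-elevation risks.

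Two broader conclusions might be drawn and should not be. One is that none of the three counts measures change: the aldolase rule is a normal-to-high shift and the raised-baseline CK rule is a fold-change, so this is true of troponin I alone. The other is that the three rules are incompatible: they are inconsistent, but each marker is reported on its own and no count combines them. For CK, it is enough to note that the raised-baseline flag depends on a single pre-dose value.

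This should be corrected, but it is a reporting weakness in a descriptive study and does not threaten the primary endpoints.

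**What to change.** Amend the PCI table in SAP 12.2 before database lock, giving both markers the two-branch structure CK already has.

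- **Troponin I:** report baseline at or below ULN with a post-baseline value above ULN as its own row. Report subjects with baseline above ULN separately, counted only if they rise by a pre-specified multiple of baseline.
- **Aldolase:** keep the existing row and add one for baseline above ULN, using a pre-specified multiple of baseline.
- **Denominators:** give each row's percentage over the subjects eligible for it by baseline status.
- **CK:** leave as it is, with a note that the raised-baseline flag rests on one pre-dose value.

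The sponsor should choose and justify the multiple. The 2 x baseline element in the protocol's ALT/AST and creatinine monitoring rules (3.7.2, 3.7.3) is only a loose precedent, because there it is combined with a multiple of ULN. These are reporting cut-offs and do not touch the management of subjects.

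The cost is a few lines of SAP text and a few table rows from data already being collected. The aldolase count may look slightly less favourable.

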12.3. DUAL ENERGY X-RAY ABSORPTIOMETRY (DXA) SCAN

Summaries of DXA data will only be presented from the start of REN001-202 and from the start of REN001 treatment.

Observed, change from baseline and percent change from baseline values for the DXA endpoints will be summarized for the DXA set. The summary will be presented overall within the group and by sex and menopausal status (i.e., men, pre-menopausal women and post-menopausal women).

A box and whisker plot will be presented for each of the parameters measuring the total spine and the 2 hip regions (total and femoral neck), for the DXA set. The whiskers will display the 5th and 95th percentiles and outliers will be identified on the plot with subject ID. The plot will present the visits alongside one another for each group. The plot will be repeated by sex and menopausal status.

For the DXA set, the study day of the follow-up DXA scans (Months 6, 30 and 54 relative to the start of REN001-201) will be summarized using descriptive statistics.

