- Option 2: Enrolment at the STRIDE FU visit: The STRIDE FU visit will be regarded as the baseline visit for this study with additional assessments performed as noted in [Section 6.1.2](#). If a washout period for any prohibited medication started since the STRIDE Week 24 visit, the subject will exit the STRIDE study and will require additional screening and baseline visits to enter the STRIDE AHEAD Study (Option 3 enroller).
- Option 3: Enrolment after exiting Study REN001-101 or STRIDE (mtDNA-PMM subjects): separate screening and baseline visits will be required, with assessments performed as noted in [Section 6.1.3](#).
- Option 4: Enrolment of nDNA-PMM subjects: separate screening and baseline visits will be required, with assessments performed as noted in [Section 6.1.4](#). nDNA-PMM subjects will not be enrolled in France.

Prior to dosing, the PSOC will assess if nDNA-PMM subjects have the appropriate diagnosis for entry into this study.

After the baseline visit each subject will have 10 scheduled visits over a period of 48 months (12 for subjects at sites in Germany). The final follow-up will be conducted by a telephone call approximately 30 days after the last dose of study drug. A final follow-up telephone call will not be required if mavodelpar has been approved within the country and the subject switches to commercially available medication.

Where sites permit, a concierge service will be available to subjects to arrange hotel accommodation and transport to and from the study centre and reimburse any subject study expenses, if applicable. Subjects may be asked to have a negative COVID-19 test prior to undertaking scheduled visits to the study centre.

All protocol assessments are detailed in the study Schedule of Activities ([Table 3](#)).

Statistical Methods:

No formal statistical testing is planned.

Endpoints will be summarized by STRIDE treatment (REN001 or Placebo) from the start of STRIDE for mtDNA-PMM subjects. Endpoints will also be summarized from the start of REN001-202, and from the start of REN001 treatment for mtDNA-PMM subjects. Subjects with nDNA-PMM will be summarized from the start of REN001-202.

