8 STATISTICAL METHODS

A formal Statistical Analysis Plan (SAP) will be finalized prior to locking the study database. The full details of data presentations and analyses will be provided in the SAP. Additional statistical analyses other than those described in this section may be performed if deemed appropriate and included in the SAP. Any deviations from the final SAP will be discussed in the final Clinical Study Report.

As this study is the open-label extension study to STRIDE, the two studies will be reported together. In addition to data being presented from the start of REN001-202, the data will also be presented from the start of STRIDE and from the start of REN001 treatment for mtDNA-PMM subjects. This will allow the assessment of long-term safety and efficacy from the start of dosing in STRIDE for those who received REN001 in STRIDE, as well as from the start of REN001 in this study.

Presentations from the start of REN001-202 will include all mtDNA-PMM subjects who receive at least one dose of REN001 in this study. The presentations will be split by the various options for entering the study, and by the STRIDE treatment group (REN001, Placebo) for those subjects who participated in STRIDE. nDNA-PMM subjects will also be summarized from the start of REN001-202.

Presentations from the start of STRIDE will include all mtDNA-PMM subjects who receive at least one dose of study drug in the STRIDE study. These will be split by the STRIDE treatment groups (REN001, Placebo). For those subjects who are enrolled into this study after exiting STRIDE only the data collected in STRIDE will be summarized in these presentations.

Presentations from the start of REN001 treatment will summarize the data emergent during treatment with REN001. These summaries will include all mtDNA-PMM subjects who receive REN001 in STRIDE and/or this study.

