8.1.3 Analysis Populations

Separate safety and full analysis sets will be identified for the different approaches to summarizing the data (start of REN001-202, start of STRIDE or start of REN001 treatment). Precise details of the analysis sets are dependent on the approach and will be defined further in the SAP, but the general definitions are:

Screened Set	All subjects who sign the informed consent form.
Safety Set/Full Analysis Set (FAS)	All subjects who receive at least one dose of study treatment .
PK Set	All subjects in the FAS who have at least 1 evaluable post-dose PK measurement (even if this is <Level of

	Quantification (LOQ) in this study.
Scan Set	All subjects in the FAS who have evaluable post-baseline DXA endpoint data.

Safety and efficacy analyses will be based upon the Safety and FAS analysis sets, respectively.

After all the data have been verified/coded/entered into the database, a review will be performed. The purpose of this review will be to define the analysis populations. The review will also check the quality of the data, identify outliers, and make decisions on how to deal with any data issues (e.g., missing values, withdrawals, protocol deviations). After the pre-analysis review, resolution of all issues and documentation of all decisions, the database will be locked.

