7.3. FULL ANALYSIS SETS

There will be a separate full analysis set (FAS) from the start of REN001-202 and from the start of REN001-201 approaches for summarizing the data.

- from the start of REN001-202 – will include all REN001-202 subjects who signed the REN001-202 informed consent form, completed screening, received at least one dose of mavodelpar study medication in REN001-202 and have not been subsequently discontinued from the study for failing eligibility criteria.
- from the start of REN001-201 – will include all subjects who signed the REN001-201 informed consent form, completed screening, received at least one dose of

study medication in REN001-201 and have not been subsequently discontinued from the study for failing eligibility criteria.

Subjects will be analysed according to the treatment they were assigned at REN001-201 randomization for the ‘from the start of REN001-201’ analyses. The FAS will be the primary analysis set for efficacy.

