13. INTERIM ANALYSES

An interim synoptic CSR will be prepared for this study to be included in the regulatory submission package. The data cut will be the date of the last subject last visit in REN001-201 and the data will be extracted from the database after REN001-201 database has been locked. This CSR will include all REN001-202 data up to the data cut date and best efforts will be made to clean data up to this data cut date.

There will be a reduced set of safety outputs generated after submission for the 120-day safety update which is required as part of the submission package. The final CSR will occur after all subjects have had the ability to complete REN001-202, the data has been cleaned and the database locked.

An independently chaired Safety Review Committee (SRC) will review safety data at specified intervals for the duration of the study. The structure, function and operation of the SRC is detailed in the REN001-202 SRC charter. The SRC review of safety data will be limited to data from REN001-202 and will not be combined with REN001-201 data.

**14. CHANGES FROM PLANNED ANALYSES SPECIFIED
IN THE PROTOCOL**

None.

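### SAP 12.3 omits the DXA summary from the start of STRIDE by randomised arm that the protocol plans, so no DXA table shows BMD change on placebo, and SAP 14 declares no change

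*SAP*

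**What the plan says.** **Protocol.** The synopsis (Statistical Methods) says: "Endpoints will be summarized by STRIDE treatment (REN001 or Placebo) from the start of STRIDE for mtDNA-PMM subjects". It continues: "Endpoints will also be summarized from the start of REN001-202, and from the start of REN001 treatment for mtDNA-PMM subjects". Protocol 8 repeats that "the data will also be presented from the start of STRIDE and from the start of REN001 treatment for mtDNA-PMM subjects", and says that the presentation from the start of STRIDE covers every mtDNA-PMM subject dosed in STRIDE, split by STRIDE treatment group. Protocol 8.1.3 adds: "Separate safety and full analysis sets will be identified for the different approaches to summarizing the data". It names all three approaches and leaves the precise definitions to the SAP. Protocol 8.2.3 sets a baseline for each approach, for safety and efficacy alike. BMD by DXA is a listed exploratory endpoint (3.2.4) with a bone-health objective (2.4).

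**SAP.** Section 8.2 makes all three approaches the default unless stated otherwise. Section 12.3 states otherwise for DXA: "Summaries of DXA data will only be presented from the start of REN001-202 and from the start of REN001 treatment". For efficacy, section 7.3 says: "There will be a separate full analysis set (FAS) from the start of REN001-202 and from the start of REN001-201 approaches". Section 10 limits the efficacy summaries to those same two approaches. Section 2 undertakes that changes from the protocol's analyses will be identified in the SAP. The entry in SAP 14, whose title begins "CHANGES FROM PLANNED ANALYSES SPECIFIED", is None.

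**The concern.** Protocol 1.4.2.6 says it is not known whether REN001 affects BMD, and that any change will be assessed with DXA where available. STRIDE is randomised and placebo-controlled, and its DXA sub-study scanned subjects at Screening and Week 24. That interval is the only time in the two studies when BMD is measured in a concurrent group not taking the drug.

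The omitted presentation is the one that would show it. Without it, a fall in BMD over months or years on mavodelpar cannot be separated, in any planned DXA table, from a fall due to age or disease. A drug effect in the first six months would also be built into the baseline of the STRIDE mavodelpar roll-overs in the REN001-202 tables. Because SAP 14 reports no change, a reader who relies on it would not learn that a protocol presentation was dropped.

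**Working it through.** The plan gives no figure to reproduce: SAP 8.1 plans no formal testing and SAP 3.5 gives no statistical basis for the sample size. The check sets the documents side by side.

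**1. Presentations for mtDNA-PMM subjects**

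| Data | Protocol | SAP | Missing from SAP |
|---|---|---|---|
| DXA | 3 | 2 (12.3) | start of STRIDE |
| Efficacy | 3 | 2 (7.3, 10) | start of REN001 |
| Laboratory bone markers | 3 | 3 (12, 12.2) | none |

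Omissions declared in SAP 14: 0 of 2.

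**2. Scan times.** SAP 6.3 gives scans at Screening and Months 6, 30 and 54 from the start of REN001-201. On the REN001-202 clock the last three are Baseline, Month 24 and Month 48.

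**3. From the start of REN001-202.** Week 24 and FU roll-overs use the STRIDE Week 24 scan as baseline (Protocol 4.4, 6.1.1 and 6.1.2; SAP 8.6). For the STRIDE mavodelpar arm that scan follows about six months on drug. Former placebo subjects have their own column (SAP 8.2, Group 1), but the change shown there is change on mavodelpar. Where a Week 24 scan exists, the placebo subjects' STRIDE screening scan enters no DXA summary.

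**4. From the start of REN001.** SAP 8.2 gives one column over all subjects. Counted from first mavodelpar dose:
- STRIDE mavodelpar arm, Week 24 and FU roll-overs: Months 6, 30 and 54.
- STRIDE placebo arm after switching: 30 − 6 = Month 24 and 54 − 6 = Month 48.

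SAP 8.4 assigns DXA scans to nominal visits without windowing, so these two cohorts share no follow-up visit. Adjacent visits in the pooled column come from different people.

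**5. From the start of REN001-201 (omitted).** Both arms have a pre-drug Screening baseline and the same visits. Screening to Month 6 compares mavodelpar with placebo. The Month 6 scan may fall up to 28 days after the visit, possibly after mavodelpar has started; SAP 6.3 regards this as too short to matter. At Month 30 the arms have had about 30 and 24 months of drug, and at Month 54 about 54 and 48, so those visits compare early with delayed start. Exit subjects contribute STRIDE data only (SAP 8.2).

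**6. Analysis set.** SAP 7.5 requires a valid REN001-202 Month 24, Month 48 or early-termination scan. A Month 6 arm comparison on that set would be selected on an event after randomisation.

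**7. Precision at Month 6.** Half-width of the 95% interval for a difference in mean percent change = 1.96 × SD × √(2/n). The documents give neither n nor SD, so both are assumed:
- n = 50 per arm, SD 2%: 1.96 × 2 × √(2/50) = 0.78 points
- n = 20 per arm, SD 4%: 1.96 × 4 × √(2/20) = 2.48 points

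**The case against.** The strongest reply is that the protocol's commitment on DXA is generic. Protocol 8.6 asks only for DXA summaries over all subjects and by sex and menopausal group, Protocol 4.4 makes the STRIDE Week 24 scan the baseline for this study, and the SAP states its restriction openly. The STRIDE scans also belong to a separate sub-study, and the documents do not show whether its Month 6 comparison appears in REN001-201 reporting. These points bear on how serious the gap is. They do not withdraw a presentation that the synopsis and Protocol 8 apply to endpoints without exception, and they do not make the entry in SAP 14 correct. REN001-201 reporting could cover Month 6 but not Months 30 and 54.

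Stronger readings are tempting, and the documents do not support them:
- A reader might infer that no bone table has a placebo column. BSAP, parathyroid hormone, vitamin D and urine NTx are reported for every safety set (SAP 12, 12.2), and the tables from the start of REN001-201 have REN001 and placebo columns (SAP 8.2).
- A reader might infer that only the from-STRIDE presentation aligns scan times. From the start of REN001-202 the roll-overs also share them: Baseline, Month 24 and Month 48.
- A reader might infer that restoring the table gives a placebo control to Month 54. Only Screening to Month 6 is placebo-controlled.
- A reader might infer that a pooled efficacy table from first dose is needed. Protocol 8 explains its plan thus: "This will allow the assessment of long-term safety and efficacy from the start of dosing in STRIDE" for those given REN001 there, and from the start of REN001 in this study. The SAP supplies both strands in separate tables. Pooling them would mix blinded with open-label results on effort-dependent tests, count some Exit subjects twice and re-baseline previously exposed REN001-101 subjects. Efficacy is descriptive only (SAP 2).

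**Conclusion.** The point holds for DXA. The SAP provides two of three planned presentations, omits the only one that keeps the randomised arms from a pre-drug baseline, and declares no change. No planned DXA table shows BMD change on placebo. This should be corrected, because the bone objective rests on DXA and the scans are already scheduled or collected.

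The restored Month 6 comparison would be modest in precision, about ±0.8 to ±2.5 percentage points under the assumed 20 to 50 scanned subjects per arm and SD of 2 to 4%. It would be descriptive and would not rule out small effects. The conclusion about what is missing does not depend on those assumptions.

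For efficacy the finding is one of documentation: the full analysis set and summaries from the start of REN001 were dropped without being listed as a change.

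**What to change.** - **SAP 12.3:** add DXA summaries from the start of REN001-201 by STRIDE arm, with the REN001-201 screening scan as baseline. Label Month 6 as the placebo-controlled comparison. Label Months 30 and 54 as early versus delayed start, for Week 24 and FU roll-overs only.
- **SAP 7.5:** define a DXA set for this presentation containing all dosed REN001-201 subjects with a baseline scan and any valid post-baseline scan. Keep the current set for the other two presentations.
- **SAP 14:** replace the present entry. List the omission of the efficacy summaries and full analysis set from the start of REN001, with the reason. A pooled efficacy table is optional. If the DXA presentation is still left out on purpose, list that too, with its reason.

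The cost is SAP text, one more analysis-set flag and regrouped versions of existing table shells; no new scans are needed. The drawbacks are small numbers, since DXA is optional and limited to approved sites, and possible overlap with REN001-201 reporting at Month 6.
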